c. Study duration and number of study visits required of research participants.

For Intervention Arm:

Study participants would be engaged for approximately 12-14 months. This time period would involve the delivery of the family-oriented DPP (or control group would receive DPP) lifestyle intervention, during which we would have 3 study-specific visits (at baseline, 6 months and 12 month data points).

For Concurrent Control Group (Control Arm):

Study participants would be engaged for one telephone-based survey administration call.

d. Blinding, including justification for blinding or not blinding the trial, if applicable.

We will not be blinding participants in this pilot study. It would not be feasible to blind participants in the 2 different arms/groups, as they are receiving different interventions (Family DPP versus being enrolled in the DPP).

e. Justification of why participants will not receive routine care or will have current therapy stopped.

Not applicable; the DPP itself is deemed routine care for adults with prediabetes, and enrollment in DPP does not interfere with receipt of other routine medical care. The family-oriented version of the DPP (FDPP) will consist of all elements of the DPP, with additional augmentations with respect to family or child-oriented content, as described earlier, and similarly will not interfere with receipt of other routine medical care for adults or children.

f. Justification for inclusion of a placebo or non-treatment group.

We have revised our study protocol from the original version (dated 4/20/22), to enroll all eligible study participants in the intervention arm. But we will plan on enrolling adult DPP participants with children under the age of 18 in a concurrent control group. This concurrent control group would consist of adult participants of the Brancati Center’s DPP program

who are living in a household with children. In this control group, we would examine adults' attendance and DPP outcomes related to weight loss and physical activity group. This would enable us to preliminarily explore differential impact of the FDPP versus DPP on adult health outcomes, informing elements of a larger comparative effectiveness trial comparing the FDPP versus the DPP.

g. Definition of treatment failure or participant removal criteria.

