Exclusion criteria for adults will reflect CDC national DPP exclusion criteria. Specifically, adults will be excluded if they are: 1) pregnant; 2) have end-stage renal disease; 3) have type 1 or type 2 diabetes. They will also be excluded if they are concurrently enrolled in a structured weight management program.

Children for whom the eligible adult is a primary caregiver (parent or guardian who cares for the child 3 or more days out of the week), will be considered eligible participants if 1) they are aged 5 through 12 years at time of recruitment; 2) they do not have a medical condition which leads to inability to comply with general pediatric dietary or physical activity goals; and 3) they are not concurrently enrolled in a structured weight management program.

Concurrent Control Group

Inclusion criteria for adults in the control group will include meeting all of the following:

- 1) Participant in the Brancati Center's Diabetes Prevention Program, in a group that has started within 6 months of Intervention Arm group start
- 2) Lives with a child less than 18 years of age in their household

5. Drugs/ Substances/ Devices – Not applicable

6. Study Statistics

a. Primary outcome variable.

Primary outcomes will examine process measures.

These will include:

- I. Feasibility measures (measuring recruitment, retention and measurement of outcomes, cost):
 - a. Recruitment rate, measured as % of eligible caregivers consented to study/time
 - b. Caregiver attendance, defined as % of adult, child-focused and all sessions attended
 - c. Child attendance, defined as % of sessions requiring child participation attended
 - d. Survey administration, defined as mean time for administration of surveys
 - e. Total cost per group of program delivery
- II. Acceptability measures
 - a. Including mean scores on Likert scale-based questions re: satisfaction with program content & structure, willingness to recommend to others
- III. Fidelity, as measured by a fidelity checklist that will be completed by a study team member observing the child-focused sessions (specifically, the child-focused sessions delivered to adult participants), and will include measures:
 - a. % of tasks/content delivery per session from coach checklist
 - b. Total & average scores per domain from observer checklist

b. Secondary outcome variables.

Secondary outcome variables will preliminarily examine:

1. Proximal intervention targets

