 - a. Caregiver (adult participant) knowledge and attitudes towards healthy-related behaviors
 - b. Perceived self-efficacy for behavioral change
 - c. Parenting self-efficacy for behavioral change
 - d. Family Home Environment
2. Caregiver (adult participant) Health behaviors and health outcomes
 - a. Physical activity- total minutes of moderate/vigorous physical activity in weeks preceding and whether caregiver meets DPP physical activity goal of 150 minutes/week of moderate-vigorous physical activity; and dietary
 - b. Dietary patterns

- c. Percent weight loss from baseline
- 3. Child health behavior and health outcomes
 - a. Physical activity- minutes/day
 - b. Screen time (hours/day)
 - c. Fruit and vegetable intake
 - d. Sugary beverage intake
 - e. Sleep duration and sleep behaviors
 - f. BMI z-score change
- c. Statistical plan including sample size justification and interim data analysis.

As the main objective of this study is evaluating FDPP feasibility and acceptability measures, sample size is primarily informed by budgetary constraints and our experience recruiting individuals for the DPP as well as recruitment for the study thus far.

Feasibility, acceptability and fidelity measures will be analyzed with descriptive statistics (Table 2). Intervention targets will be analyzed as continuous variables (means or numerical scores). Caregiver and child health behaviors will be analyzed as continuous variables (average value/day) and a binary variable (achievement of goal). The caregiver health outcome will be modeled as a continuous variable (percent of weight loss from baseline) and binary variable (achievement of 5% weight loss goal). The child health outcome is the BMI Z-score, a continuous variable. Within-groups, we will use 1) paired-t tests to analyze pre-post changes (from baseline to 6 months and baseline to 12 months) of continuous variables; and 2) McNemar's exact test to examine pre-post changes in proportion achieving behavioral and outcome goals (binary variables). Between groups, we will use 1) 2-sample t-tests to compare the magnitude of mean group change in values of continuous variables; and 2) Fisher's exact test to compare proportion achieving goals at 6 and 12 months. If continuous variables do not meet distribution assumptions necessary for use of parametric tests (t-tests), we will use appropriate non-parametric tests (Mann-Whitney test or, for paired data, Wilcoxon signed-rank test).

- d. Early stopping rules.

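### McNemar's test is assigned to the 5% weight-loss goal, which nobody can have met at baseline, so its within-group p-value is uninformative

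*Combined protocol and SAP*

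**What the plan says.** Section 6c treats the caregiver health outcome in two forms: a "continuous variable (percent of weight loss from baseline) and binary variable (achievement of 5% weight loss goal"). It then prescribes, within groups, McNemar's "exact test to examine pre-post changes in proportion achieving behavioral and outcome goals (binary variables").

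The outcome goals in that clause can only be the 5% weight-loss goal. The other health outcome has no goal and is not binary: "The child health outcome is the BMI Z-score, a continuous variable". Nothing elsewhere in the document exempts the 5% goal or gives it another within-group summary.

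Between groups, the plan uses Fisher's "exact test to compare proportion achieving goals at 6 and 12 months". Section 6b introduces these outcomes as exploratory: "Secondary outcome variables will preliminarily examine". Section 3f says the control group is there to "preliminarily explore differential impact of the FDPP versus DPP on adult health outcomes", which is a between-group aim.

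**The concern.** McNemar's test compares the proportion of yes answers before and after in the same people. It uses only those who changed and asks whether changes from no to yes and from yes to no are equally likely. That question makes sense only if both answers are possible at both times.

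For the 5% goal they are not. Every adult has lost 0% at baseline, so nobody can move from yes to no. Equal proportions before and after would mean a true success rate of zero, which no one needs a test to reject once a single adult succeeds. The resulting p-value says nothing about how large the success rate is.

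Weight is collected in both arms (section 3a, data collection), so a reader could set the two within-arm p-values side by side and take them as evidence on how well each programme worked.

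**Working it through.** The documents state no sample size, significance level or p-value for this goal, so there is no figure of the plan's own to reproduce. The arm sizes and the two-sided 0.05 threshold below are assumptions.

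**Inputs**
- Binary outcome: 5% weight loss, yes or no, counted from baseline (section 6c).
- Within-group test: McNemar's exact test (section 6c).
- Time points: baseline to 6 months and baseline to 12 months. Section 6c attaches these to the paired t-tests; applying them to McNemar's test is the natural reading of the same sentence.

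**Formula.** Let b be the number who met the goal at baseline only and c the number who met it at follow-up only. The two-sided exact p-value is min(1, 2 × P(X ≥ max(b, c))), with X ~ Binomial(b + c, 0.5). Here b = 0 by definition and c = k, the number of achievers. So P(X ≥ k) = 0.5^k and

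p = min(1, 2 × 0.5^k).

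| Achievers k | p |
|---|---|
| 1 | 1.0 |
| 2 | 0.5 |
| 3 | 0.25 |
| 4 | 0.125 |
| 5 | 0.0625 |
| 6 | 0.03125 |

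At 0.05 the test therefore asks only whether at least six adults reached the goal.

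**Six achievers at three assumed arm sizes**

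| Adults analysed | Proportion | Exact (Clopper-Pearson) 95% interval | McNemar p |
|---|---|---|---|
| 15 | 6/15 = 40% | 16.3% to 67.7% | 0.031 |
| 30 | 6/30 = 20% | 7.7% to 38.6% | 0.031 |
| 60 | 6/60 = 10% | 3.8% to 20.5% | 0.031 |

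The p-values can also rank arms the wrong way round. Five achievers among 10 (50%) give p = 0.0625, while six among 60 (10%) give p = 0.031.

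**Contrast with a goal that can be met at baseline**, such as 150 minutes of activity a week. Six gains with 0, 1, 2 or 3 losses give p = 0.031, 0.125, 0.289 and 0.508. The losses carry information and the test responds to them. For the 5% goal that cell is always empty.

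**Number of p-values affected:** 2 arms × 2 follow-up times = up to 4.

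**The case against.** The strongest reply is that the consequence is small. The outcome is secondary and examined only in a preliminary way. The primary process measures are descriptive, there are no stopping rules, and no progression decision hangs on this p-value. Fisher's test requires the proportions at 6 and 12 months in any case. All of that stands and limits the weight of the point, but it does not make the test valid.

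A second reply is that insensitivity to the number analysed belongs to every exact McNemar test, because people who do not change never enter it. That is correct, so the table by arm size does not by itself show the fault. The fault is the cell that is empty by construction: the null is trivially false, and p = 1.0 for one achiever shows it.

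Third, controls may be recruited when already in a DPP group (section 3a). If before meant study entry while loss was counted from programme start, some controls could already have met the goal. Section 6c uses a single baseline for both, so this is the less natural reading, and it does not reach the intervention arm.

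Finally, an interval and a count of missing weights go beyond deleting the test, and the plan specifies no intervals elsewhere. That is fair. But once the test goes, the proportion needs a statement of precision, and it cannot be read without its denominator.

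**Conclusion.** The concern holds. As written, section 6c applies McNemar's test to a goal whose baseline proportion is zero by definition, and the resulting p-value depends only on the count of achievers: 1.0 for one, 0.031 for six. This follows from the definition of the goal and needs no assumption about sample size. The arm sizes in the illustration and the 0.05 threshold are assumed. The count of up to four p-values rests on applying the stated time points to this test in both arms.

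The reach is narrow: one within-group test of one secondary outcome. Fisher's comparison, the percent-loss analysis, the primary process measures and the between-group aim in section 3f are unaffected, and McNemar's test remains suitable for behavioural goals that can be met at baseline. It should be corrected, because following the plan would put an invalid p-value into the results.

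**What to change.** Replace the McNemar clause in section 6c with:

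> Within groups, McNemar's exact test will be used for behavioral goals that can be met at baseline. For the 5% weight-loss goal no pre-post test will be done; we will report the number and proportion achieving it in each arm at 6 and 12 months with an exact (for example Clopper-Pearson) 95% confidence interval, stating the denominator and the number of adults without a weight at that time.

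Leave Fisher's between-group test as it is. The cost is one sentence in the statistical plan. The weights are already collected, so data collection and recruitment do not change.

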- The FDPP has been developed as an *augmented* version of the DPP. That is, adult participants would receive all the above-mentioned elements of the DPP intervention (delivered in the same manner as the DPP intervention), with a few augmentations that are not intended to alter the evidence-based DPP program, but rather supplement it to address caregivers’ own lifestyle change efforts while having children at home AND to introduce basic concepts regarding healthy child habits related to dietary intake, physical activity and screen time, and sleep. This supplementation/augmentation is achieved via:
 - Addition of content to certain DPP sessions that will ensure barriers to/facilitators of lifestyle change that other family members (including children) pose to adult participants are discussed.
 - Addition of 2 supplementary sessions during the core period that will specifically discuss making lifestyle changes while being the caregiver of children and explore how family members, including children, serve as motivation for lifestyle change.
 - Child-focused sessions in the “post-core” period of the DPP (see supplementary material which includes proposed schedule), which will be delivered to adult participants, and accompanied by separate sessions for children. Adults and children will first present together for the child-focused sessions, then separate, and come together at the end. At the end, adults and children will convene to discuss what they learned and come up with basic child or family health behavior goals related to the health behaviors. These sessions discuss pediatric guidelines or recommendations endorsed by the American Academy of Pediatrics or other relevant national society (e.g., Centers for Disease Control and Prevention, American Heart Association), and will also cover strategies and tips to enable caregivers to support children in achieving these goals. The topics to be covered will include:
 - MyPlate (discussing MyPlate guidelines, and how to achieve variety and balance in meals for children)
 - Fruit and Vegetables (discussing guidelines around children’s intake and tips and strategies to increase fruit and vegetable intake)
 - Sleep (discussing sleep recommendations, including how to promote sound sleep of good quality in children)
 - Reducing Sugary Beverages (discussing sugar intake guidelines and how to promote healthier beverage consumption)

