For child participants, screening eligibility will be conducted via the adult participant. It is possible, given the definition of caregiver that is used, that the caregiver may not be able to answer specific questions regarding the child's inclusion criteria. If this is the case, the child's parent or legal guardian will be contacted to confirm the child's eligibility.

If a caregiver has more than 1 child in the eligible age range, the study team member conducting the screener will use a random number generator to select one child randomly, and assess the eligibility of this child. If the child is not eligible, then the next child's eligibility will be assessed. If the caregiver expresses a strong desire to assess the eligibility of a certain child in particular, then the study team member will be advised to start with the eligibility screening of this child.

Enrollment of the Intervention Arm

- Enrollment of adult participants (and child participants) in the intervention arm, after eligibility screening, completion of adult consent process and the child assent (with parent or legal guardian consent) process (Details regarding consent and assent as detailed in Sections 14-17 of the eIRB application).
- Any related enrollment processes related to the adult participant's participation in the DPP as routine care, will be conducted by the Brancati Center team as per routine practices for DPP enrollment.
- For the child, the enrollment form will confirm parent/legal guardian contact information (emergency contact information), the child's pediatrician, and food or other allergies to be aware of.

Randomization

- Participants will not be randomized to the intervention. All participants who are recruited for the intervention arm will be engaged in the FDPP intervention.

Recruitment and Screening Eligibility: Concurrent Control Group (Control Arm)

Recruitment of Concurrent Control Group (Control Arm):

The concurrent control group will consist of adults in the Brancati Center's DPP (who started the program within 6 months of the Intervention group) and who have children less than 18 years of age living in their household. We will recruit adult participants for the concurrent control groups through several means as detailed in "Section 13." This will include

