1) Recruitment from adults currently participating in Brancati Center DPP groups (which have started within 6 months of the Intervention Arm groups): During a DPP session, participants will be read a brief paragraph regarding the concurrent control group as follows and a flyer will also be distributed to group participants via email:

"There is a research study for DPP participants that you may be eligible for. This study involves adults in the DPP who have children less than 18 years living in their household. As part of the study, you would be asked to complete surveys once. The study team would also compare participants' DPP attendance and outcome data with that of other adult participants who are enrolled in a Family Diabetes Prevention Program pilot study. You would be compensated for your time."

If potential participants are interested, their contact information would be provided to the Family DPP study team; contact information of the study team would also be provided.

2) Recruitment from adults who are to start a Brancati Center DPP program: Individuals who are enrolled in (assigned to a DPP group, but not yet started) will be read the following during routine telephone calls conducted prior to group start:

"There is a research study for DPP participants that you may be eligible for. This study involves adults in the DPP who have children less than 18 years living in their household. As part of the study, you would be asked to complete surveys once. The study team would also compare participants' DPP attendance and outcome data with that of other adult participants who are enrolled in a Family Diabetes Prevention Program pilot study. You would be compensated for your time. Would you be interested in learning more about this study?"

Screening eligibility for the Concurrent Control Group (Control Arm)

Potential adult participants will be screened for eligibility for the concurrent control group by the study team via telephone.

Intervention Delivery (Family DPP)

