The DPP (and FDPP) interventions are designed for prevention of type 2 diabetes in adults with prediabetes. Some adult participants may progress to type 2 diabetes while participating in the FDPP; the CDC's guidelines are that these individuals can remain in the DPP lifestyle intervention (given the benefits of lifestyle modification). The Brancati Center team confers with the participant's primary care provider if this were to occur (development of type 2 diabetes) to confirm that the participant is recommended to continue in the DPP.

h. Description of what happens to participants receiving therapy when study ends or if a participant's participation in the study ends prematurely.

Participants will be instructed to continue with routine medical care when the program ends or if their participation ends prematurely.

i. If biological materials are involved, please describe all the experimental procedures and analyses in which they will be used.

Not applicable.

4. Inclusion/Exclusion Criteria

Intervention Arm

The study will enroll adult-child dyads in the Intervention Arm.

Adult inclusion criteria will include meeting all of the following:

- 1) CDC national criteria for enrollment in the DPP (as used by the Johns Hopkins Brancati Center's DPP programs):
 - Be 18 years of age or older and not pregnant at time of enrollment
 - Have a body mass index (BMI) of $\geq 25 \text{ kg/m}^2$ ($\geq 23 \text{ kg/m}^2$, if Asian American).
 - Meet either one of the criteria
 1. Have a recent (within the past year) blood test meeting one of these specifications:
 - i. Fasting glucose of 100 to 125 mg/dl (CMS eligibility requirement for Medicare DPP suppliers is 110 to 125 mg/dl)
 - ii. Plasma glucose measured 2 hours after a 75 gm glucose load of 140 to 199 mg/dl
 - iii. A1c of 5.7 to 6.4%.
 2. Clinically diagnosed gestational diabetes mellitus (GDM) during a previous pregnancy
 3. A positive screening for prediabetes based on the CDC or American Diabetes Association Diabetes Screening Test (a brief questionnaire)
- 2) being a primary caregiver of at least one eligible child aged 5 through 12 years at time of recruitment (defined as caring for the child, with a responsibility for the child's food, sleep and activity habits, at least 3 days out of the week)

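### The exploratory FDPP-versus-DPP contrast is planned as bare unadjusted tests between non-randomised arms, with no interval, no stated comparability description, and no handling of controls recruited while already attending

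*Combined protocol and SAP*

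**What the plan says.** **Allocation.** Section 3a (Randomization): "Participants will not be randomized to the intervention". Controls are recruited separately.

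**Purpose.** Section 3f gives the contrast a preliminary, exploratory role on adult outcomes, to inform a larger comparative trial. The abstract adds adult attendance to what will be compared.

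**Analysis.** Between groups, section 6c specifies "2-sample t-tests to compare the magnitude of mean group change in values of continuous variables", Fisher's exact test for goal achievement at 6 and 12 months, and Mann-Whitney if distributional assumptions fail. It names no covariate, stratification, matching or confidence interval. Descriptive statistics are assigned only to feasibility, acceptability and fidelity.

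**Comparability by design.** Both arms are served by the same DPP provider. Controls must be "in a group that has started within 6 months of Intervention Arm group start" and have a child at home. In the FDPP, "adult participants would receive all the above-mentioned elements of the DPP intervention". The first FDPP recruitment route draws on the same DPP outreach that supplies controls who have not yet started.

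**Differences by design.** Section 4 requires of FDPP adults "being a primary caregiver of at least one eligible child aged 5 through 12 years at time of recruitment"; of controls it requires "Lives with a child less than 18 years of age in their household". FDPP adults may also come through flyers, paid advertising and provider referral. Controls come by two routes. For groups already running, "During a DPP session, participants will be read a brief paragraph regarding the concurrent control group", with a flyer emailed to the group. Adults yet to start "will be read the following during routine telephone calls conducted prior to group start".

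**Data on both arms.** Attendance, weight and activity minutes come from the DPP database (section 3b), along with routine screening, enrolment and demographic data (section 3a). Surveys in both arms cover household demographics, child demographics and social determinants. Controls are surveyed once (section 3c).

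**The concern.** A two-sample test on change answers a question about the program only if the arms would have changed alike under the same program. Randomisation would justify that; here nothing does beyond partial matching by design. The outcome's starting value enters the change score, but differences in caregiving role, household circumstances and route into the study do not.

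The most specific threat is recruitment in session. An adult who hears the announcement in a running group has started and is still coming. An emailed flyer can reach an absent member, but still only one whose group has begun. Early non-attenders are thus likely to be under-represented among these controls, while FDPP dropouts are all counted. This would tend to raise control attendance and, if attendance goes with weight loss, control weight loss too. Adults who answer an advert for a family program may be unusually motivated, which pushes the other way, so the net direction is not known.

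At stake is what the contrast contributes to the larger trial. A p-value with no estimate, interval or picture of who is in each arm is a poor basis for that trial's effect size or design.

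**Working it through.** The plan states no sample size, SD, alpha or effect size, so there is no figure of its own to reproduce. The text check is the set of sections cited above. The arithmetic below only illustrates scale, and **every input is assumed**.

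**1. Bias from one unadjusted factor.** Bias = imbalance (SD units) × correlation with percent weight change × SD of percent weight change.
- Central: 0.5 × 0.3 × 5 = 0.75 points (0.15 SD).
- Low: 0.25 × 0.2 × 5 = 0.25. High: 0.75 × 0.4 × 5 = 1.5.

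**2. Effect on the test, and precision.** With no true effect, the rejection rate of a nominal 5% two-sided test comes from the noncentral t with noncentrality 0.15 × √(n/2) and 2n − 2 degrees of freedom. The 95% CI half-width is t × 5 × √(2/n).

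| n per arm | Rejection rate | Half-width (points) |
|---|---|---|
| 10 | 6.2% | 4.70 |
| 20 | 7.5% | 3.20 |
| 30 | 8.8% | 2.58 |
| 40 | 10.2% | 2.23 |

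Imprecision exceeds the central bias at every size shown.

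**3. What adjustment buys.** Simulation, 20,000 runs per cell, central case, no true effect. The model contains arm, the confounder or a proxy for it, and two noise covariates. Unadjusted bias is about 0.75 throughout.

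| Covariate available | Bias left, n = 10/20/30/40 | RMSE unadjusted | RMSE adjusted |
|---|---|---|---|
| Confounder itself | −0.01/0.00/0.00/0.02 | 2.35/1.74/1.50/1.37 | 2.44/1.62/1.31/1.13 |
| Proxy, correlation 0.5 | 0.55/0.56/0.57/0.58 | 2.34/1.75/1.49/1.36 | 2.50/1.74/1.44/1.28 |
| Proxy, correlation 0.3 | 0.64/0.70/0.68/0.69 | 2.34/1.76/1.48/1.34 | 2.54/1.80/1.48/1.32 |

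The data held are broad survey and enrolment items, so the proxy rows are the realistic ones. There adjustment helps little at 10 to 30 per arm.

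**4. Adjusting a change score for its own baseline.** Suppose the arms differ stably by d SD, the pre-post correlation is r, and there is no effect. The change-score difference is then unbiased, and the baseline-adjusted difference is biased by d × (1 − r).
- d = 0.5, r = 0.5: 0.25 SD.
- Range: 0.25 × (1 − 0.8) = 0.05 SD to 0.5 × (1 − 0.4) = 0.30 SD.

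This can exceed the 0.15 SD in step 1. If the arms instead regress to a common mean, the ranking reverses. The documents cannot say which applies.

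**5. Timing of the control survey.** Controls recruited from running groups answer their single survey after starting. Although it is called a baseline survey, only routine screening and enrolment data are clearly pre-program in both arms. Activity minutes are collected during the program, so a first recorded value may also fall after start.

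**The case against.** The strongest reply is that this is an exploratory contrast in a feasibility pilot. The protocol says so repeatedly, makes process measures primary and claims no causal effect. That stands, and it limits the weight of the point. It does not explain planning tests without estimates, since exploratory work is where intervals and a comparability table are most useful.

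Second, on the illustrative numbers the bias is smaller than the sampling error, and proxy adjustment barely improves accuracy. That also stands. Adjustment therefore belongs in a secondary place, shown beside the unadjusted difference.

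Third, the arms are closer than the eligibility lists suggest, because one FDPP route shares its source with the pre-start controls. This is correct, although the share of participants from each route is not stated. It also supports a pre-start-only analysis, where that overlap is strongest.

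Fourth, silence on a baseline table in an IRB application is weak evidence that none will be made. Agreed: 6c does not rule one out, and it cites a Table 2 that is not in the supplied text. What is missing is a commitment, in particular to splitting controls by when they were recruited.

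**Conclusion.** The point holds for the between-arm contrast on adult outcomes. Section 6c, followed literally, gives unadjusted tests between arms that differ in eligibility and recruitment, with no estimate and interval and no stated use of the background data. Recruitment of controls already attending is the leading problem, and covariate adjustment cannot remove it. The amendment is worth making, but this is not a fault in the study's main purpose.

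Three stronger readings might be inferred and are not supported:
- That the primary results are compromised. Feasibility, acceptability and fidelity within the FDPP do not depend on the controls; only the attendance comparison with controls is affected.
- That the contrast is biased by a known amount. The 0.75 points rest on an assumed SD of 5, imbalance of 0.5 SD and correlation of 0.3, and the sample sizes are assumed too.
- That regression adjustment would put it right. With proxies most of the illustrative bias remains, and adjusting for the outcome's own baseline can add bias in non-randomised arms.

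**What to change.** Amend section 6c as follows.

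1. Report each between-arm difference (attendance, percent weight change, activity minutes, goal proportions) with a 95% CI. Label the contrast exploratory and non-causal.
2. Tabulate characteristics by arm, with controls split by recruitment before or after their group started. Use routine DPP screening and enrolment data as the true baseline, and note that the control survey may have been completed after start.
3. Repeat the contrast using only controls recruited before group start, above all for attendance.
4. As a secondary analysis beside the unadjusted difference, give one pre-specified adjusted difference with 95% CI, using one or two pre-program or stable covariates held in both arms. The survey forms are not in the supplied text, so the items need confirming. If the outcome's own baseline is included, show that result beside the change-score result. Present neither as definitive.
5. Optionally, restrict controls to those with a child aged 5-12 at home.

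**Cost.** Wording, one table and a little programming, with no new data items; recruitment timing relative to group start must be identifiable for each control. In the simulations the adjusted CI was about 10-11% wider at an assumed 10 per arm, 3-4% at 20 and 1-3% at 30. Restricting controls costs more. If half qualify (assumed), the half-width t × 5 × √(1/n + 1/m), with m = n/2 and n + m − 2 degrees of freedom, rises from 4.70 to 5.92 points at n = 10, 3.20 to 3.97 at 20, and 2.58 to 3.19 at 30.
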